14.3.3 Exploratory analyses

Cognitive function (MoCA-scores) will be compared using the Mann-Whitney test, and time until decline of MoCA-scores will be compared. Associations between biomarkers in tissue, blood and stool samples, and treatment outcomes, baseline characteristics, and survival will be investigated. A detailed project plan including biomarker and data analysis plan will be defined when sufficient biological material and clinical data to start the translational research have been collected.

14.3.4 Interim analyses

The Safety and data monitoring committee will perform an interim analysis when 2/3 of the target number of patients (n≥85 in both arms) have completed a minimum of three chemotherapy courses (and TRT in the experimental arm). According to the O'Brien-Fleming approach, an alpha of 0.0054 will be allocated to the interim analyses. Consequently, enrolment will be stopped if the survival difference is statistically significant with a 2-sided p≤0.0054. If enrolment continues beyond the interim analysis, the significance level for the primary survival analysis is p≤0.0492.

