An independent Safety and data monitoring committee will perform an interim analysis when 2/3 of the target number of patients ($n\ge 85$ in both arms) have completed a minimum of three chemotherapy courses (and TRT in the experimental arm). According to the O'Brien-Fleming approach, an alpha of 0.0054 will be allocated to the interim analyses. Consequently, enrolment will be stopped if the survival difference is statistically significant with a 2-sided p ≤ 0.0054 . If enrolment continues beyond the interim analysis, the significance level for the primary survival analysis is p ≤ 0.0492 .

The sample size calculation was performed using SPSS Sample Power v3.

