14.3.2 Efficacy analyses

For the primary endpoint, the Cox proportional hazards method will be used to compare survival between the treatment groups. Considering that median overall survival was 12-13 months in the two trials that established chemo-immunotherapy as treatment of ES SCLC, the study is designed to perform the primary survival analyses 14 months after last patient entry (to ensure that all survival data at 1 year are captured), which is a timepoint when we believe that the first signal of an effect of the experimental treatment can be seen. Additional survival analyses will be performed 2-, 3-, 4- and 5-year after last patient entry.

Median OS, PFS and time to progression in the brain will be estimated using the Kaplan-Meier method, and a Cox-model will be used for multivariable analyses adjusting for established prognostic factors in the target population (sex, PS, disease stage, presence of brain metastases and liver metastases) and age. Pearson's Chi-square test will be used to compare response rates (overall and in non-irradiated lesions), frequency of brain metastases, and location of metastases.

All HRQoL scores will be transformed to a scale of 0-100 according to the EORTC QLQ scoring manual. Mean scores will be compared at each assessment timepoint. A difference of 10 points is considered clinically relevant. Primary HRQoL-endpoints are dyspnea, global quality of life and physical function. All other HRQoL-scales will be included in complementary analyses.

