14.4 Determination of sample size

[figure not shown]
The sample size calculation assumes an accrual period of 30 months and that the primary survival analysis is performed 14 months after last patient entry. Additional survival analyses will be performed 2, 3, 4 and 5 years after last patient entry. All patients will be followed for a maximum of 5 years when the final survival

analysis will be performed.

Furthermore, the calculation is based on a constant hazard ratio of 0.65, corresponding to median survival times of 13.10 months for the control group and 20.02 months for the experimental group, and 1-year survival rates of 53% in the control group and 66% in the experimental group. This effect was selected as an effect of clinical relevance and an effect of this magnitude might be anticipated if there is a synergistic effect of combining radiotherapy with durvalumab.

The criterion for significance (alpha) has been set at 5%. The test is

2-tailed, which means that an effect in either direction will be interpreted. For this study design, alpha and tails, the population effect size described above, and to have power of 80% to yield a statistically significant result, 128 patients are required in each treatment group.

Enrolment will continue until 128 or more patients in the control arm have completed minimum three chemo-immunotherapy courses, and minimum 128 patients in the experimental group have completed minimum three chemo-immunotherapy courses plus TRT of 30 Gy. We expect a loss to follow-up and inability to complete three courses (plus TRT in the experimental group) of maximum 15% and estimate that we need to enroll a total of 302 patients.

All eligible patients who are randomized will be included in the primary efficacy analyses (ITT-population). All patients who commence chemo-immunotherapy will be included in the toxicity analyses. In addition, we will perform analyses of the patients who complete minimum three chemo-immunotherapy courses (and TRT in the experimental arm) (per protocol population). The sample size calculation was performed using SPSS Sample Power v3.

15. Ethical and regulatory requirements

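### The final significance level of 0.0492 is slightly too high for an interim level of 0.0054: the pair is not O'Brien-Fleming at 2/3 and spends 5.02% there, about 5.0-5.2% over plausible timings

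*Protocol*

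**What the plan says.** Section 14.4 fixes the overall level: "The criterion for significance (alpha) has been set at 5" percent, two-tailed. Section 14.3.4 places the single interim look "when 2/3 of the target number of patients (n≥85 in both arms) have completed a minimum of three chemotherapy courses", plus thoracic radiotherapy in the experimental arm. It continues: "According to the O'Brien-Fleming approach, an alpha of 0.0054 will be allocated to the interim analyses". Enrolment stops if the two-sided p for the survival difference is at or below that level. Otherwise, "If enrolment continues beyond the interim analysis, the significance level for the primary survival analysis is p≤0.0492". The synopsis repeats both levels ("an alpha of 0.0054 will be allocated to the interim analyses").

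The test is time-to-event. Under section 14.3.2, "the Cox proportional hazards method will be used to compare survival between the treatment groups". The timing inputs are in section 14.4, which "assumes an accrual period of 30 months and that the primary survival analysis is performed 14 months after last patient entry". The look is defined only by patient counts. Neither place gives an information fraction in deaths or a rule for adapting the final level to the one observed.

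**The concern.** Three things are fixed together: the method (O'Brien-Fleming), the timing (2/3) and the two levels. They do not fit one another. At 2/3 an O'Brien-Fleming design spends noticeably more at the interim and leaves a lower final level than the protocol states.

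An interim level stricter than the named method requires does no harm to the type I error. A final level that is too generous for what has been spent does. Since 0.0492 is the threshold for the trial's primary claim, the question is whether the pair holds the stated two-sided 5%, at 2/3 and at the death fraction where the look would really fall.

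**Working it through.** **Inputs.** Levels 0.0054 and 0.0492 (section 14.3.4); two-sided 5%, 30-month accrual, analysis at month 30 + 14 = 44, control median 13.10 months, hazard ratio 0.65, 128 per arm, 302 enrolled, 15% loss or non-completion (section 14.4).

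**Are the levels O'Brien-Fleming?** The two-sided critical values are 2.782 and 1.967. Classical O'Brien-Fleming requires c1 = c2/√t, so the pair implies t = (1.967/2.782)² = 0.4998, the shape of a halfway look.

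- At t = 2/3: 0.0142/0.0452 (classical) or 0.0121/0.0463 (Lan-DeMets).
- At t = 1/2: 0.0052/0.0480 (classical), so the stated final level does not fit there either.
- In the classical design, 0.0054 is the interim level at t = 0.506 (final 0.0479), while 0.0492 is the final level at t = 0.403 (interim 0.0019). With Lan-DeMets the two points are 0.558 and 0.480.

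The two levels therefore belong to different looks.

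**Overall error.** Error = 1 − P(|Z1| < 2.782, |Z2| < 1.967), bivariate normal with correlation √t.

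| Information fraction t | Error of 0.0054/0.0492 | Final level holding 5% with 0.0054 kept |
|---|---|---|
| 2/3 | 5.02% | 0.0490 |
| 0.60 | 5.06% | 0.0486 (0.04855) |
| 0.50 | 5.13% | 0.0479 |
| 0.40 | 5.20% | 0.0472 |
| 0.36 | 5.22% | 0.0469 |

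The error falls to 5.00% at t = 0.7025. A simulation of 20 million draws at t = 2/3 gave 0.05022.

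**Where the look falls in deaths.** Hazards are λc = ln 2/13.10 = 0.0529 and λe = 0.65 × λc = 0.0344 per month. With uniform accrual, the probability of death by month 44 is 1 − (e^(−14λ) − e^(−44λ))/(30λ), which gives 0.761 (control) and 0.615 (experimental).

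As a check on the model, 128 × (0.761 + 0.615) ≈ 176 deaths, for which the Schoenfeld formula gives 81.5% power. The stated 128 per arm thus reproduces. Enrolment of 302 gives 151 × (0.761 + 0.615) ≈ 208 deaths.

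The look needs 85 completers per arm. At 85% completion that is 85/0.85 = 100 enrolled per arm, reached at 100/151 × 30 = month 19.9. With 256 enrolled and full completion it is 85/128 × 30 = month 19.9 as well. The third course is at week 6 (schedule in section 2), so the lag from entry of the last required patient to the look is at least 1.4 months. I allow up to 6 months for delays, data cleaning and committee preparation. The protocol does not state this lag, so the range is an assumption.

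For a look at month T, expected deaths per arm = 151 × (T/30) × [1 − (1 − e^(−λT))/(λT)], summed over arms:

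- 302 enrolled, HR 0.65: about 74 of 208 deaths at a 1.4-month lag (t = 0.36), 84 at 3 months (0.40), 103 at 6 months (0.50). Error 5.22% to 5.13%.
- 302 enrolled, no effect: 86 to 119 of 230 (0.37-0.52). Error 5.21% to 5.12%.
- 256 enrolled, HR 0.65: 63 to 88 of 176 (0.36-0.50). Error 5.22% to 5.13%.
- 302 enrolled, HR 0.65, follow-up censored at 12 months: 64 to 83 of 122 (0.53-0.68). Error 5.11% to 5.01%.

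**The case against.** The strongest reply concerns size. At 2/3, the only fraction the protocol gives, the excess is 0.02 percentage points and the total rounds to 5.0%. Everything larger comes from modelled death fractions and an assumed lag. That is correct, and it is why the point is minor. But the excess at 2/3 needs no timing assumption.

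Second, the named endpoint is 1-year survival, so censoring at 12 months is a natural reading. Under it, t reaches 0.7025 and the excess vanishes at a lag of about 6.6 months. Both arms must also reach 85 completers, so the slower arm decides. Allowing for chance, that happens at about month 20.5 on average, and a 6-month lag then gives t of about 0.70. This stands: under that reading the low end of the range is no inflation. If all deaths count, as in an uncensored Cox comparison, the excess persists until a lag of about 11.5-12 months.

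Third, the protocol says only that enrolment stops at an interim crossing. The calculation treats a crossing as a rejection, which is the usual reading but is not spelled out.

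Finally, a statistical analysis plan could refine the method. It could not use another final level without contradicting a threshold the protocol fixes twice.

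**Conclusion.** The concern holds, as a minor one. The stated method, timing and levels cannot all be right, and 0.0492 is slightly too high after a 0.0054 interim at any information fraction below about 0.70, including the stated 2/3. The overall two-sided error is 5.02% at 2/3 and about 5.0-5.2% over the timings considered. The upper part of that range rests on uniform accrual, exponential survival at the protocol's medians and a lag of 1.4 to 6 months. The practical consequence is confined to a final p-value between the level that holds 5% (about 0.047-0.049, depending on timing) and 0.0492.

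**What to change.** In section 14.3.4 and the synopsis:

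1. Express the look as deaths observed over deaths planned for the primary analysis, and say whether deaths after 12 months count.
2. Keep 0.0054. Replace 0.0492 with the final level that holds a two-sided 5% at the observed death fraction, by a rule fixed before interim data are seen. As a guide, this is 0.0490 at 2/3, 0.0479 at 1/2, 0.0472 at 0.40 and 0.0469 at 0.36. Round down in use: 0.0490 at 2/3 spends 5.002%, so strict control there means 0.0489.
3. Drop or qualify the O'Brien-Fleming label, since 0.0054 with a corrected final level is still not that boundary at 2/3. Deriving both levels from a spending function would make the label true, but it also changes the chance of stopping early and is not needed to control the error.

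The cost is wording in two places. Power lost at HR 0.65 (208 deaths with 302 patients, 176 with 256) is 0.04-0.05 percentage points at 2/3, 0.24-0.31 at 1/2, 0.36-0.47 at 0.40 and 0.41-0.53 at 0.36. The interim rule and its chance of stopping enrolment do not change.

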14.4 Determination of sample size

[figure not shown]
The sample size calculation assumes an accrual period of 30 months and that the primary survival analysis is performed 14 months after last patient entry. Additional survival analyses will be performed 2, 3, 4 and 5 years after last patient entry. All patients will be followed for a maximum of 5 years when the final survival

analysis will be performed.

Furthermore, the calculation is based on a constant hazard ratio of 0.65, corresponding to median survival times of 13.10 months for the control group and 20.02 months for the experimental group, and 1-year survival rates of 53% in the control group and 66% in the experimental group. This effect was selected as an effect of clinical relevance and an effect of this magnitude might be anticipated if there is a synergistic effect of combining radiotherapy with durvalumab.

The criterion for significance (alpha) has been set at 5%. The test is

2-tailed, which means that an effect in either direction will be interpreted. For this study design, alpha and tails, the population effect size described above, and to have power of 80% to yield a statistically significant result, 128 patients are required in each treatment group.

Enrolment will continue until 128 or more patients in the control arm have completed minimum three chemo-immunotherapy courses, and minimum 128 patients in the experimental group have completed minimum three chemo-immunotherapy courses plus TRT of 30 Gy. We expect a loss to follow-up and inability to complete three courses (plus TRT in the experimental group) of maximum 15% and estimate that we need to enroll a total of 302 patients.

All eligible patients who are randomized will be included in the primary efficacy analyses (ITT-population). All patients who commence chemo-immunotherapy will be included in the toxicity analyses. In addition, we will perform analyses of the patients who complete minimum three chemo-immunotherapy courses (and TRT in the experimental arm) (per protocol population). The sample size calculation was performed using SPSS Sample Power v3.

15. Ethical and regulatory requirements

15.1 Ethical conduct of the study

The study will be performed in accordance with ethical principles that have their origin in the Declaration of Helsinki and are consistent with ICH GCP, and applicable regulatory requirements Patient data protection.

15.2 Ethics and regulatory review

Approval from all relevant national and local regulatory authorities will be collected before enrolment starts.

15.3 Informed consent

Informed consent of each subject will be obtained through a written and verbal explanation process that addresses all elements required by ICH GCP. Sponsor will develop a core ICF for use by all investigators in the clinical study. The National Coordinating Investigator in each country will, based on this core ICF, be responsible for developing an ICF in all official languages in their country which complies with local and national laws and regulations.

The Principal Investigator(s) at each center will:

- Ensure each subject is given full and adequate oral and written information about the nature, purpose, possible risk and benefit of the study.
- Ensure each subject is notified that they are free to discontinue from the study at any time.
- Ensure that each subject is given the opportunity to ask questions and allowed time to consider the information provided.
- Ensure each subject provides signed and dated ICF before conducting any procedure specifically for the study.
- Ensure the original, signed ICFs are stored in the Investigator's Site File.
- Ensure a copy of the signed ICF is given to the subject.

 Ensure that any incentives for subjects who participate in the study as well as any provisions for subjects harmed due to study participation are described in the ICF.

15.4 Changes to the protocol and ICF

Study procedures will not be changed without the mutual agreement of the Principal Investigator and sponsor. Any changes will be documented in a study protocol amendment.

For a substantial change to the protocol, the sponsor will distribute amended versions of the protocol to all investigator(s). Before implementation, amended protocols, including revised ICD, must be approved by the relevant local and national regulatory authorities. Any non-substantial changes will be communicated to all relevant regulatory authorities.

15.5 Audits and inspections

Authorized representatives of a Competent Authority and IRB/REB/IEC may visit the centers to perform inspections, including source data verification. Likewise, the representatives from sponsor may visit the centers to perform an audit. The purpose of an audit or inspection is to systematically and independently examine all study-related activities and documents to determine whether these activities were conducted, and data were recorded, analyzed, and accurately reported according to the protocol, Good Clinical Practice (ICH GCP), and any applicable regulatory requirements. The principal investigator at each study site will ensure that the inspectors and auditors will be provided with access to source data/documents.

16. Study management

16.1 Training of study site personnel

A site initiation visit will be performed at all sites before study start. Training will include walkthrough of the protocol, study procedures, CRF, study drug management, and reporting of AEs. Furthermore, all personnel who will perform the MoCA test will need to complete the online training. All study procedures will be described in a study procedure manual.

16.2 Monitoring of the study

16.2.1 Source data

The study will be monitored according to a separate monitoring plan.

16.3 Study timetable and end of study

We expect to enroll the first patient in Q1 2022, and to complete enrolment in Q2 2024. According to this schedule, the analyses for the primary endpoint will be performed in Q3 2025. All patients will be followed for a maximum of 5 years, and we expect to complete follow-up in Q2 2029.

17. Data management

The trial will be conducted in compliance with the protocol, ICH GCP and the applicable regulatory requirements. The staff at the central trial office at NTNU in Trondheim will oversee that data are collected and stored appropriately. The investigators must maintain adequate and accurate records to enable the study to be conducted according to protocol and fully documented, including but not limited to the protocol, protocol amendments, ICFs, and documentation of EC and governmental approval.

All patients will provide a written informed consent before any data are collected. The study personnel will enter data required by the protocol into the electronic, web-based Case report forms (WebCRF). Participants will be assigned a unique study ID at each site. All data recorded and transferred will be linked to this ID, no personal data will be stored in the CRF or transferred to the central trial office.

The web-based CRF has been developed in close collaboration between the Central Study Management, the protocol committee and the Unit for Applied Clinical Research, NTNU.

During study conduct, the data are stored on a secure server at the St. Olavs hospital with

restricted access. According to current regulations for clinical medical research, all data will be transferred to the Norwegian Centre for Research Data and stored for 15 years after study completion. All personally identifiable data will then be deleted.

The investigators are responsible for assuring that data entered in the CRF is complete, accurate, and that entry is performed in a timely manner, and no later than 2 weeks after each visit, procedure or AE. The CRF enables the central study management in Trondheim, in collaboration with monitors, to monitor data entry and send reminders if data are not entered within a reasonable timeframe.

The protocol specifies how SAEs, SUSARs and AESIs should be defined and reported. All SAE, SUSAR and AESI reports will immediately be reviewed by the medical personnel at the central trial office and complementary information will be requested when needed.

